8. SAFETY ANALYSES

The safety analyses will be based on the ITT population. However, if there are more than 5% of subjects who receive a rituximab/placebo infusion that is different from the randomized treatment for one or both doses, safety analysis will be performed on the As Treated population.

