10.2. Sample Size Determination

In order to ensure adequate exposure for evaluation of safety, the study is designed with a target of 140 participants to be randomized into the combination arm. At least 280 participants will be randomised in this study, with a target of 70 participants in Arm A, 140 participants in Arm B and 70 participants in Arm C. This sample size provides at least 98% power (for the comparison of Arm B to Arm A at Week 52) at the 5% level of significance assuming the underlying response in the control arm is 10% and the true population effect is ≥25% with treatment Arm B (combination assumed response rate of 35%). The primary endpoint will be based on assuming study dropouts = treatment failures, and so the assumed responder rates for treatment Arms A and B already account for participant dropout rates. However, the sample size may be increased up to a maximum of 320 participants if the dropout rate, missing data or number of major protocol deviations suggests further participants are necessary to ensure robust conclusions can be drawn. Sample size was calculated using PASS 12 and is based in the Likelihood ratio test. No inferential tests are planned between Arm C and Arm A or Arm B; therefore no adjustment for multiplicity is required.

There are limited clinical data with therapies including both belimumab and rituximab. Based on elicitation of opinion from external experts, as well as the rarity of remission or disease control seen in published external studies and internal GSK review of previous belimumab data, a rate of 35% achieving a state of disease control (i.e., Arm B) is considered to be highly significant in SLE care. The assumed 10% responder rate in Arm A (control) at 52 weeks was estimated based on exploration of historical data from three comparable belimumab Phase 3 trials (IV: C1056 [BLISS-76] and C1057 [BLISS-52] and SC: BEL112341) in patients with SLE, albeit with some significant differences from this study in protocol inclusion criteria, control of background therapy for SLE, SLEDAI-2K derivation and treatment failure rules. The estimated Arm A

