10.3. Populations for Analyses

For purposes of analysis, the following populations are defined:

Population	Description
Enrolled	All participants who sign the ICF.
Randomized	All participants who are randomized. This population will be comprised of participants according to the treatment that a participant was randomized to receive, regardless of the actual treatment received.
Intent-To-Treat (ITT)	All randomized participants who received at least one dose of study treatment. This population will be comprised of participants according to the treatment that a participant was randomized to receive, regardless of the actual treatment received.
Modified Intent-	Arm A&B: All randomized participants who received at least one dose of study

Population	Description
To- Treat (MITT)	treatment will be included.
	Arm C: All randomized participants who received at least one dose of study treatment and for whom their independent blinded assessor was not potentially unblinded (i.e., enrolled after 07SEPT 2018) will be included.
	This population will be comprised of participants according to the treatment that a participant was randomized to receive, regardless of the actual treatment received.
Per-Protocol (PP)	All randomized participants who receive at least one dose of study treatment excluding participants with major protocol deviations with potential to impact efficacy assessments.

All further populations to be used for the assessment of health outcomes, biomarkers and pharmacokinetics data will be defined in the RAP.

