10.4.2. Safety Analyses

All safety analyses will be performed on the ITT Population.

Endpoint	Statistical Analysis Methods
Secondary	Descriptive statistics will be used to summarize AEs, SAEs, AEs of special interest (AESI), changes in laboratory parameters, and immunogenicity (both antibelimumab and anti-rituximab antibodies will be assessed). The frequency of laboratory abnormalities will be tabulated by treatment group. The frequency of AEs will be tabulated by MedDRA system organ class (SOC) and preferred term and compared between treatment arms.

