4. ANALYSIS POPULATIONS

During the early conduct of the study some participants in ARM C (n=29) were inappropriately identified on a laboratory report which could have unblinded the independent blinded assessors. Blinding of Arms A and B was not compromised. For this reason the sample size was increased, and a Modified Intent To Treat (MITT) population has been created to exclude the potentially unblinded (to the independent blinded assessor) Arm C subjects.

| Population | Definition / Criteria | Analyses Evaluated |
|---------------------------------|---|---|
| Screened (Enrolled) | 
 All screened candidates who sign the ICF | 
 Screen failures and Study Population |
| Randomized | 
 All participants who were randomly assigned to treatment in the study. Any participant who receives a treatment randomization number will be considered to have been randomized. This population will be based on the treatment the participant was randomized to. | 
 Study Population |
| Intent-To-Treat (ITT) | 
 All randomized participants who received at least one dose of study treatment (Belimumab or Rituximab/placebo) . This population will be based on the treatment the subject was randomized to. | 
 Study Population Safety Pharmacodynamic and Biomarker |
| Modified Intent-To-Treat (MITT) | 
 All randomized participants who received at least one dose of study treatment (Belimumab or Rituximab/placebo) . Arm C subjects randomized prior to 07 September 2018, whose independent blinded assessor had potential to be unblinded, are excluded from this population. This population will be based on the treatment the subject was randomized to. | 
 Efficacy Health Outcomes |
| Per Protocol (PP) | 
 All participants in the MITT population who comply with the protocol. Protocol deviations that would exclude participants from the PP population are defined in Section 4.2 (Per Protocol Population) and Appendix 1: Protocol Deviation Management and Definitions for Per Protocol Population. The PP set will not be analysed if this population comprises more than 85% of the MITT population. | 
 Efficacy |

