| As Treated | 
 All randomized participants who received at least one dose of study treatment (Belimumab or Rituximab/placebo) . Subjects in Arms A or B who receive one or more infusions of rituximab will be included in Arm B for the As Treated analysis. Subject in Arm B who receive two doses of rituximab-placebo (and no rituximab) will be included in Arm A. | 
 If more than 5% of subjects received the incorrect RTX treatment, then the Primary efficacy endpoint will be repeated for this population Safety endpoints if more than 5% received the wrong RTX |

| | | |
|----------------------|---|---|
| | | treatment, then this population will replace the ITT for safety |
| Pharmacokinetic (PK) | 
 All participants in the ITT population who had at least 1 non-missing PK assessment (Non-quantifiable [NQ]. values will be considered as non-missing values). | 
 PK |

The following additional populations will be defined as pre-COVID-19 populations. The COVID-19 environment onset date is defined in Section 15.6.16.

| Population | Definition / Criteria | Analyses Evaluated |
|--------------------------------|---|--|
| MITT Week 52 prior to COVID-19 | 
 All randomized participants who received at least one dose of study treatment and had their first dose of study medication early enough that they should have completed their Week 52 visit prior to the COVID-19 environment onset date, i.e. their first dose of study treatment was prior to the onset date minus 52 weeks Arm C subjects randomized prior to 07 September 2018, whose independent blinded assessor had potential to be unblinded, are excluded from this population This population will be based on the treatment the subject was randomized to. | 
 Efficacy |

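### Safety tables stay grouped by randomised arm unless more than 5% of subjects receive the wrong infusion, and the base of that 5% is not defined

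*SAP*

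**What the plan says.** Protocol Section 10.4.2 is unconditional: "All safety analyses will be performed on the ITT Population". Protocol Section 10.3 groups that population "according to the treatment that a participant was randomized to receive, regardless of the actual treatment received".

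SAP Section 8 starts from the same place ("The safety analyses will be based on the ITT population"), and SAP Section 4 says of the ITT set: "This population will be based on the treatment the subject was randomized to". Section 8 then adds a switch to the As Treated population, which applies "if there are more than 5% of subjects who receive a rituximab/placebo infusion that is different from the randomized treatment", for one or both doses. The As Treated entry in Section 4 repeats the trigger ("Safety endpoints if more than 5% received the wrong RTX" treatment) and says that the population then replaces ITT for safety.

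The grouping rule for that population is: "Subjects in Arms A or B who receive one or more infusions of rituximab will be included in Arm B". An Arm B participant moves to Arm A only after two placebo infusions and no rituximab.

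Neither section defines the denominator of the 5%. Below the trigger, no as-treated safety table is specified, even as a supplement. The end-of-study addendum (July 2021, Section 2.1.7) places every safety table on ITT or ITT Year 2.

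**The concern.** Harm is normally attributed to the drug a person received. The SAP accepts this above 5% but gives no reason why it should not apply at or below 5%. With one to several mis-infused controls, the adverse event, serious adverse event and AESI tables would show rituximab-exposed people in the column that is read as unexposed. Arm B participants who received only placebo would likewise stay in the rituximab column. If rituximab raises a risk, both errors shrink the apparent excess.

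This comparison matters here. Protocol Section 10.2 sized the combination arm for safety exposure. Sections 3.3 and 3.3.1 describe experience with co-administration as very limited and list serious and opportunistic infection, hypogammaglobulinaemia, PML and hepatitis B reactivation as risks. Some of these are rare enough that one event in the wrong column could change how a table reads.

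**Working it through.** **Inputs.** Arm sizes come from Protocol Section 10.2 ("with a target of 70 participants in Arm A, 140 participants in Arm B and 70 participants in Arm C"). They are consistent with the power of at least 98% stated there: 70 against 140 at 10% and 35%, two-sided 0.05, gives 98.9% by a pooled z test and 99.0% by exact enumeration of the likelihood ratio test. The plan gives no figure on mis-infusion to reproduce. Event risks are assumptions. The nearest figures in the protocol (Section 3.3.1) are serious infection rates of 4% per year for rituximab in rheumatoid arthritis and 5% for belimumab or placebo in SLE, and these do not establish any particular gap.

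**Step 1: how many errors leave the tables as randomised.** The limit is the largest whole number not exceeding 5% of the base.

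- Base Arms A and B: 0.05 × 210 = 10.5, so up to 10. All in Arm A: 10/70 = 14.3%.
- Base all participants: 0.05 × 280 = 14, so up to 14. All in Arm A: 14/70 = 20.0%.
- At the maximum size of 320 (80, 160 and 80 by the 1:2:1 ratio): 0.05 × 240 = 12, or 15.0% of 80; 0.05 × 320 = 16, or 20.0% of 80.

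Only Arms A and B receive infusions, so including Arm C in the base loosens the rule.

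**Step 2: effect on the comparison.** Let f be the share of Arm A wrongly given rituximab, with true risks pA without rituximab and pB with it. The observed Arm A risk is pA + f(pB − pA). With Arm B unaffected, the observed difference is (1 − f)(pB − pA). If a share g of Arm B received only placebo, the observed Arm B risk is pB − g(pB − pA).

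With pA = 4% and pB = 10%, and 10 errors spread 70:140 as 3.33 in Arm A and 6.67 in Arm B (4.8% of each):

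| Scenario | Observed Arm A | Observed Arm B | Difference (points) |
|---|---|---|---|
| No errors | 4.00% | 10.00% | 6.0 |
| 10 errors, all in Arm A | 4.86% | 10.00% | 5.1 |
| 14 errors, all in Arm A | 5.20% | 10.00% | 4.8 |
| 10 spread; Arm B cases had two placebo infusions | 4.29% | 9.71% | 5.4 |
| 10 spread; Arm B cases still had one rituximab infusion, taken to carry full risk | 4.29% | 10.00% | 5.7 |

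**Step 3: other assumed risks, all errors in Arm A.** With 5% and 10%, the difference of 5.0 points becomes 4.3 (10 errors) or 4.0 (14 errors), and the risk ratio of 2.00 becomes 1.75 or 1.67. With 5% and 15%, the difference of 10.0 becomes 8.6 or 8.0, and the ratio of 3.00 becomes 2.33 or 2.14.

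**Step 4: scale against sampling error.** At 4% and 10% with 70 and 140 participants, the 95% half-width of the difference is 1.96 × √(0.04 × 0.96/70 + 0.10 × 0.90/140) = 6.8 points.

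**The case against.** The strongest case against the point is that it concerns something that may never have happened. Placebo is locally sourced saline, rituximab comes in labelled vials, an unblinded pharmacist prepares the infusions, and unblinded monitors review the pharmacy records (Protocol Sections 7.1 and 7.4). Errors in the 5% count in both directions, so 14.3% and 20% are one-directional extremes. Even the worst shift at 4% and 10% (6.0 − 4.8 = 1.2 points) is well inside the 6.8-point half-width, and the protocol's safety analysis is descriptive. The SAP's switch already goes further than the protocol.

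A reader might also infer that exposed controls would be hidden. The documents do not support that. As Treated counts are tabulated by treatment group (SAP Section 6.2), population membership and infusion exposure are listed (Sections 6.2 and 6.5), and wrong treatment is a deviation category (Section 15.1.1).

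These arguments limit the size of the point. They do not remove it. Traceability in listings does not correct the arm-level tables, and sampling error does not excuse a known direction of bias that costs almost nothing to avoid. One further objection also stands: the As Treated rule is not ready to use as written. It does not place an Arm B participant who had a single placebo infusion and no rituximab, or no infusion at all.

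**Conclusion.** The point holds as a cheap improvement to the plan. At or below an undefined 5%, safety tables follow randomisation, and events in a rituximab-exposed control are tabulated under belimumab plus placebo. The worst case is 14.3% or 20% of Arm A, depending on the base, and the same share of the true risk difference is lost. Under the assumed 4% and 10%, that leaves 5.1 or 4.8 of 6.0 points. A proportional spread of 10 errors leaves about 5.4 to 5.7.

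These figures rest on target arm sizes, assumed risks, full risk after any rituximab infusion, and errors reaching the limit. It would be wrong to conclude that mis-dosing took place, that a loss of this size is expected, or that the reported safety comparison is unreliable. Nothing in the documents shows a single wrong infusion.

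**What to change.** In SAP Section 8 and the As Treated entry of Section 4, drop the 5% threshold and present safety by the As Treated population. At minimum, require As Treated versions of the key adverse event, serious adverse event and AESI tables whenever any participant is mis-infused. If a threshold is kept for any purpose, state its denominator.

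Complete the As Treated rule for Arm B participants with one placebo infusion and no rituximab, and for those with no infusion. Align Protocol Section 10.4.2 and the populations in Section 2.1.7 of the end-of-study addendum. That addendum was written after the first database lock, so a change made now should be labelled as such.

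The cost is a small amount of redrafting and a documented departure from the protocol's ITT statement. If no wrong infusion occurred, and once the rule covers every Arm B case, the tables are the same as the ITT tables.

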8.1. Adverse Events

8.1.1. Reporting Phases

Adverse events will be reported for Year 1 and Year 2 study period:

8.1.1.1. Pre Treatment

Adverse events starting prior to the 1st dose of belimumab.

8.1.1.2. On Treatment (Year 1 only)

As defined in Section [5.12](#)

8.1.1.3. On Study

As defined in Section [5.11](#)

Year 2 reporting will include all events starting on or after Week 52 visit + 1 day and at or prior to the Week 104 visit.

Year 1&2 reporting will include all events starting on or after the 1st dose of belimumab and at or prior to the Week 104 visit.

The tabular summary for each category of AE listed below will include the number of events, number of subjects who reported at least one event, and percentage of subjects who reported at least one AE (incidence) by treatment group for each SOC (where applicable), each PT, and overall.

8.1.1.4. Post Withdrawal/Completion

Adverse events starting after the on study period (Section [5.11](#) / Section [8.1.1.3](#)) will be reported separately.

8.1.2. Adverse Events Analyses

- Adverse events analyses including the analysis of adverse events (AEs), Serious Adverse Events (SAEs) and AEs of special interest (AESIs) will be based on GSK Core Data Standards.
- All subjects will be followed for safety through at least 8 weeks post-treatment.

- A table summarizing AEs that occurred prior to treatment start date will be presented, for each system organ class (SOC) and preferred term (PT) by treatment group [T13.01].
- All AEs will be classified using the current standard GSK Medical Dictionary for Regulatory Activities (i.e. MedDRA version in use at the time of reporting), and grouped by SOC and PT, unless otherwise stated. MedDRA version is detailed on every table that uses MedDRA . The Year 1 report will be based on MedDRA dictionary version 23. The Year 2 report will use the MedDRA dictionary current at the time of reporting the Year 2 data (anticipated to be version 25) and hence will be different to Year 1. Dictionary coding changes between Year 1 and Year 2 will be listed (L23.13) and any impact on the interpretation will be detailed in the Year 2 clinical study report (CSR). The investigator will evaluate all AEs with respect to seriousness, severity, and causality. The severity of an AE is to be determined using the Assessment of Intensity provided in Appendix 7 of the protocol, if a grade is provided for the AE of interest.
- AEs during Year 1 that are not reported until Year 2; and AEs that have their reporting details (e.g. onset date, severity etc) changed after Year 1, will be reported in Year 2 with the latest details. Changes will be listed and summarised as appropriate.
- All treatment-emergent AEs will be summarized for both the double-blind phase (Year 1) and the observational phase (Year 2) separately. Selected tables will also be produced for Years 1 and 2 combined. See Section 8.1.1 for definitions of phases.
- An overall summary of AEs will be presented showing the number and percent of subjects with at least one: AE, related AE, serious AE (SAE), severe AE, AE resulting in study treatment discontinuation, and deaths [On Treatment:T13.02, and On Study: T13.03, T23.01,T23.02, L13.05, L13.06, L23.12].
- Common AEs will be defined as $\geq 5\%$ incidence in any treatment group.
- The number and percentage of subjects experiencing an AE and the total number of AEs will be summarized for each of the following AE categories:
 - All AEs (by SOC and PT) [On Treatment: T13.04; On Study: T13.05, T23.03, T23.04].
 - AEs (by PT) [On Treatment:T13.06; On Study: T23.05]. (ordered on total incidence – Arms A+B+C)
 - Study treatment Related AEs (by SOC and PT) – belimumab only [on Treatment:T13.07; on Study: T23.06].
 - Study treatment Related AEs (by SOC and PT) – rituximab only [on Treatment:T13.08; on Study: T23.07].
 - Study treatment Related AEs (by SOC and PT) – Both belimumab and rituximab [on Treatment:T13.09; on Study: T23.08].
 - Severe AEs (by SOC and PT) [On Treatment:T13.11, on Study T23.27].
 - Serious AEs (by SOC and PT) [On Treatment:T13.21, and on Study:T13.22, T23.19, T23.20]

- AEs leading to permanent discontinuation of study treatment (by SOC and PT) [on Study: T13.26, T13.27; on Study: T23.21, T23.22].
- Deaths (by Category and PT) [on Study: T13.20, T23.18].
- Common Non-Serious AEs (by SOC and PT) [on Study: T13.28; T23.23].
- Study treatment Related Serious AEs (by SOC and PT) [On Treatment: T13.23, T13.24, T13.25; on Study: T23.24, T23.25, T23.26].
- Fatal Serious AEs (by SOC and PT) and Study treatment Related Fatal Serious AEs (by SOC and PT) [On Treatment: T13.29; on Study: T23.28].
- By default, adverse events will be sorted by MedDRA SOCs, in descending order from the SOC with the highest total incidence (i.e., summed across all treatment groups) for any adverse event within the class, to the SOC with the lowest total incidence. If the total incidence for any two or more adverse events is equal, the events will be presented in alphabetical order. Only SOCs with observed AE PTs will be presented. Repeat sort order for MedDRA PTs within each SOC.
- The table for all AEs by SOC and PT will be repeated for the following subgroups:
 - Age group (<65, >=65), [On Treatment: T13.12; On Study: T23.10].
 - Race (Black, non-Black), [On Treatment: T13.13; On Study: T23.11].
 - Country region, [On Treatment: T13.14; On Study: T23.12].
 - Baseline C3/C4 levels & anti-dsDNA subgroup [On Treatment: T13.15; On Study: T23.13].
 - Baseline SLEDAI-2K (<=9, >=10) [On Treatment: T13.16; On Study: T23.14].
 - Baseline Immunosuppressant use (Y,N) [On Treatment: T13.17; On Study: T23.15].
 - Baseline Corticosteroid dose (<=10 mg/day, >10 mg/day) [On Treatment: T13.18; On Study: T23.16].
 - Gender, [On Treatment: T13.19; On Study: T23.17].
- For Year 1 reporting, the table of deaths by category and PT will include deaths that occurred during Year 1 and fatal SAEs that started during Year 1 and resulted in death during Year 2 by the time of the data cut [On Treatment: T13.20]. For Year 2 reporting, the table of deaths by category and PT will include deaths that occurred during Year 2 (and 8-week Follow-up) that have not been previously reported in Year 1 as a result of a fatal SAE [On Study: T23.22].
- A summary of AEs by SOC, PT and severity will also be provided by treatment group. The number and percentage of subjects will be summarized as mild, moderate or severe based on the maximum severity observed within each PT, and within each SOC [On Treatment: T13.10; On Study: T23.09].
- The hierarchical relationship between MedDRA SOCs, PTs, and verbatim text will be displayed in a listing for all AEs [L13.01, L23.01].
- A listing of all AEs [On Study: L13.02, L23.02], study treatment related AEs [On Study: L13.03, L13.04, L23.03, L23.04], and AEs resulting in study treatment

discontinuation [On Study: L13.05, L13.06, L23.05] and post withdrawal [L13.07,23.06] will be presented, including duration, study day of onset/resolution and days since 1st / last belimumab dose.

- If a Year 1 adverse events is reported after year 1 database lock it will be reported in year 2 (L23.07).
- A summary of Adverse Events including Exposure-Adjusted Incidence Rates will be produced for Year 1 On Treatment (Section 5.12) [T13.44] and Years 1&2 combined On Study (Section 5.11) [T23.37]. These will present Adverse Events Overall and by System Organ Class and Preferred Term and will display:
 - the number of subjects experiencing the event (n);
 - For Year 1: the sum of the total time to the first event or total on treatment time* if no event (years) across all subjects (e), * defined in Section 15.6.2: On Treatment Exposure (Year 1);
 - For Years 1&2 combined: the sum of the total time to the first event or total on-study time* if no event (years) across all subjects (e), * defined in Section 15.6.2: On-Study Exposure (Years 1&2 Combined);
 - the exposure adjusted subject rate per 100 subject years ($r = (n/e)*100$).
- A summary of Adverse Events leading to Permanent Discontinuation of Belimumab Study Drug including Exposure-Adjusted Incidence Rates will be produced for Year 1 On Treatment (Section 5.12) [T13.45] and Years 1&2 combined On Study (Section 5.11) [T23.39]. These will present Adverse Events Overall and by System Organ Class and Preferred Term and will display:
 - the number of subjects experiencing the event (n);
 - For Year 1: the sum of the total time to the first event or total on treatment time* if no event (years) across all subjects (e), * defined in Section 15.6.2: On Treatment Exposure (Year 1);
 - For Years 1&2 combined: the sum of the total time to the first event or total on-study time* if no event (years) across all subjects (e), * defined in Section 15.6.2: On-Study Exposure (Years 1&2 Combined);
 - the exposure adjusted subject rate per 100 subject years ($r = (n/e)*100$).

